5.3.6 Participant Withdrawal

Participants may withdraw from the study at any time for any reason. If a participant withdraws from the study after randomization but prior to receipt of the first vaccine dose administered during study procedure, sites will replace that participant in their randomization group to keep a 2:1:1 randomization scheme. Participants who wish to withdraw from the study will contact the study site principal investigator or coordinator to inform them of their decision. Upon withdrawal from the study, the participant's specimens will be destroyed and discarded if requested by study participant. The participant's data (including responses to the enrollment questionnaire, follow-up survey, and any extracted data) will be removed from all study site databases if requested by study participant.

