Study Duration:	12 months total Enrollment: Aug — Oct 2023 Vaccination: Aug — Nov 2023 Blood draws: Aug 2023 — May 2024 Active surveillance for illness: Aug 2023 — May 2024 Laboratory testing: Nov 2023 — Jul 2024
Participant Duration and Number of Participants:	
 • Up to 10 months (Aug 2023 — May 2024) • 800 total participants (600 aged 18-64 years, 200 aged 6-11 years) at 4 sites (only two sites will enroll children aged 6-11 years)
Randomization:	Adults aged 18-64 years, 2:1:1 permuted block randomization 
 i. Concomitant cclIV4 + COVID-19 mRNA (day 0) [n = 300] ii. Sequential cclIV4 (day 0), COVID-19 mRNA (day 28) [n = 150] iii. Sequential COVID-19 mRNA (day 0), cclIV4 (day 28) [n = 150]

	
Children aged 6-11 years, 2:1:1 permuted block randomization
 
 i. Concomitant ccIV4 + Moderna COVID-19 mRNA (day 0) [n = 100] ii. Sequential ccIV4 (day 0), Moderna COVID-19 mRNA (day 28) [n = 50] iii. Sequential Moderna COVID-19 mRNA (day 0), ccIV4 (day 28) [n = 50]

Description of Study Procedures:
	
This study is a randomized immunogenicity study in an enrolled cohort with active surveillance for acute respiratory illness (ARI). During this study, participants will be randomly assigned to receive an approved quadrivalent influenza vaccine (Flucelvax [ccIV4]) and mRNA COVID-19 vaccine (Moderna) either concomitantly (given in contralateral arms) or sequentially (28 days apart).
 
Blood samples from participants will be collected for measurement of biomarkers of immune response at baseline (visit 1; day 0), post-vaccination 1 (visit 2; day 28), post-vaccination 2 (visit 3; day 56), and post-season (visit 4; day 180). Serum and peripheral blood mononuclear cells (PBMC) and plasma (target to collect PBMC and plasma samples at every visit from a subset of approximately 250 participants; 200 adults and 50 children) samples will be isolated from whole blood and tested for biomarkers of vaccine immunogenicity, and duration of antibody responses.

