5.4.2 Randomization

Permuted block randomization stratified by age group (children aged 6-11 years and adults aged 18-64 years) and site will be used at each site to ensure even allocation to each study arm. At each site, participants will be randomized 2:1:1 to receive: (i) concomitant administration of a mRNA COVID-19 vaccine and a quadrivalent influenza vaccine (cclIV4), (ii) sequential administration of a quadrivalent influenza vaccine (cclIV4) at Visit 1 (day 0) and a mRNA COVID-19 vaccine at Visit 2 (day 28), and (iii) sequential administration of a mRNA COVID-19 vaccine at Visit 1 (day 0) and a quadrivalent influenza vaccine (cclIV4) at Visit 2 (day 28). The project statistician will generate the randomization schemes which will be uploaded to REDCap. Participants will be randomized through REDCap with treatment allocation recorded

on the case report form. In the event that REDCap is unavailable, participants will be manually randomized through the use of sealed envelopes with randomization allocations enclosed. The project statistician will prepare envelopes that will use the same randomization strategy as the primary scheme embedded in REDCap. When an unblinded team member is informed of the age group, they will pull the next envelope in order. To capture the allocation per subject, a separate form in REDCap will be used by the unblinded study personnel to add the assignment. Sites will need to keep a log capturing these instances. The next available sequential study-number will be assigned to each enrolled participant upon study-entry.

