## 4.3 Randomization

Permuted block randomization stratified by age group (children aged 6-11 years and adults aged 18-64 years) and site will be used at each site to ensure even allocation to each study arm. At each site, participants will be randomized 2:1:1 to receive: (i) concomitant administration of a mRNA COVID-19 vaccine and a quadrivalent influenza vaccine (cclIV4), (ii) sequential administration of a quadrivalent influenza vaccine (cclIV4) at Visit 1 (day 0) and a mRNA COVID-19 vaccine at Visit 2 (day 28), and (iii) sequential administration of a mRNA COVID-19 vaccine at Visit 1 (day 0) and a quadrivalent influenza vaccine (cclIV4) at Visit 2 (day 28).

The project statistician will generate the randomization schemes which will be uploaded to REDCap. The randomization schedule will not be available to the study staff, so the next randomization allocation will not be known before randomization occurs. Following confirmation of study eligibility criteria during Visit 1, participant randomization will be through REDCap with treatment allocation recorded on the case report form (CRF).

In the event that REDCap is unavailable, participants will be manually randomized through the use of sealed envelopes with randomization allocations enclosed. The project statistician will prepare envelopes that will use the same randomization strategy as the primary scheme embedded in REDCap. When an unblinded team member is informed of the age group, they will pull the next envelope in order. To capture the allocation per subject, a separate form in REDCap will be used by the unblinded study personnel to add the assignment. Sites will need to keep a log capturing these instances. The next available sequential study-number will be assigned to each enrolled participant upon study-entry.

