## 4.4 Blinding

Participants will not be blinded to vaccine group and will receive two vaccines in separate limbs (for the concomitant vaccination [group i]) or one vaccine at Visit 1 (day 0) and a second vaccine at Visit 2 (day 28) (for sequential vaccination [groups ii and iii]) in an unblinded manner.

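### Pre-dose withdrawals are replaced within their own arm, so as written the replacement's allocation is known before that person is enrolled

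*Protocol*

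**What the plan says.** Protocol 5.3.6 sets the trigger, "If a participant withdraws from the study after randomization but prior to receipt of the first vaccine dose administered during study procedure", and the action: "sites will replace that participant in their randomization group to keep a 2:1:1 randomization scheme". The site does the replacing, and the place to be filled is in a named arm.

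The trial is open label. SAP 4.4 states: "Participants will not be blinded to vaccine group and will receive two vaccines in separate limbs". Protocol 5.1 agrees.

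On allocation, Protocol 5.4.2 says: "Permuted block randomization stratified by age group (children aged 6-11 years and adults aged 18-64 years) and site will be used at each site". The statistician prepares the lists, and participants are allocated through REDCap, with sealed envelopes as backup. SAP 4.3 repeats this and adds: "The randomization schedule will not be available to the study staff, so the next randomization allocation will not be known before randomization occurs". Neither section mentions replacements.

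SAP 6.1 keeps everyone enrolled and randomized in the ITT population, and SAP 8.1 plans a flow chart by age and randomization group. SAP 9.1 analyses the primary objective in the immunogenicity population, which under SAP 6.3 requires receipt of both vaccines.

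**The concern.** If a site must refill a particular arm and knows which arm it is, the next person's allocation is settled before that person is approached or judged eligible. Two decisions are then made with the arm known: whom to approach, and whether the person qualifies. The second includes a discretionary exclusion based on the investigators' opinion (Protocol 5.3.2, item xv).

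The withdrawn person received no vaccine and is outside the primary analysis population. The replacement can be inside it. Neither document flags replacements or plans an analysis without them, so any selection would pass into the group i versus group ii comparison. HAI titre is a laboratory measure, so the risk is in who enters the arm and not in how the outcome is assessed.

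**Working it through.** **Planned arm sizes.** The protocol summary gives 600 adults and 200 children at 2:1:1. N × ratio / 4 gives 300/150/150 and 100/50/50, matching the stated figures. Combined, the arms are 400/200/200. The documents contain no sample-size or power calculation to reproduce.

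**Predictability.** Under same-arm replacement with a known vacated arm, the next allocation is predictable with probability 1.0. The comparison is ordinary 2:1:1 permuted blocks with all earlier allocations known. Block size is not given, so 4, 8 and 12 are assumed.

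- Block of 4: the chance that the best guess is right at positions 1 to 4 is 1/2, 1/2, 7/12 and 1. The mean is 2.583 / 4 = 0.646.
- Blocks of 8 and 12, by simulation: 0.602 and 0.580.

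Open-label blocking is already partly guessable. The replacement rule removes the remaining uncertainty for the people it covers.

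**Possible effect on the GMT.** No pre-dose withdrawal rate is given, so 1%, 2% and 5% are assumed. Let f be the fraction of an arm that is replaced and d the mean log2 titre difference between replacements and those they replace. The arm's GMT shifts by a factor of 2^(f × d). For group ii, with d = 1 or 0.5 (both assumed):

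| f | replaced of 200 | d = 1 | d = 0.5 |
|---|---|---|---|
| 1% | 2 | 1.007 | 1.003 |
| 2% | 4 | 1.014 | 1.007 |
| 5% | 10 | 1.035 | 1.017 |

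The GMT ratio of group i to group ii moves only if f × d differs between the two arms. Equal selection in both cancels.

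**What the rule buys.** Suppose each withdrawal is made up from the next concealed allocation and withdrawal does not depend on arm. The concomitant count then drifts with SD = √(800 × f × 0.5 × 0.5):

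- f = 1% (8 people): √2 = 1.4
- f = 2% (16 people): √4 = 2.0
- f = 5% (40 people): √10 = 3.2

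With no replacement at all, the standard error for 400 versus 200 grows by 1/√(1 − f), which is 0.5%, 1.0% and 2.6%.

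As a stress test, let all 16 withdrawals come from group ii, made up from the next allocations. The lists issue 816 allocations (408/204/204) and the dosed split is 408/188/204. The standard error ratio is √[(1/408 + 1/188) / (1/400 + 1/200)] = √(0.00777 / 0.00750) = 1.018. Even this one-sided case costs under 2%.

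**The case against.** The strongest reply is that the protocol does not describe how a replacement is allocated. It does not say that REDCap is bypassed or that staff pick the person. If the statistician returned the vacated slot to a concealed point in the list, the arm would not be known. That is correct, and a reader who infers that concealment has been shown to fail goes further than the documents allow. But this safeguard appears in neither document, while the instruction to sites to replace within the arm does. Nor does SAP 4.3 flatly contradict the rule: it is a general statement that does not address replacements, and the two need reconciling.

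A reader might also infer that withdrawal is likely to be driven by the arm, because sequential participants must wait 28 days for the second vaccine. The eligibility rules largely answer this. Protocol 5.3.1 requires consent to randomization among all three groups, 5.3.2 excludes people who do not agree to both schedules, and 5.3.5 has candidates view the procedures before consenting. Group i also returns at Visit 2 for blood. Arm-related withdrawal remains possible, since participants learn their arm before the dose, but the documents do not show it to be likely.

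A third tempting inference is a sizeable bias. Twenty replacements in group ii with a one-log2 difference would give 2^(20/200) = 1.072. That needs 10% of an arm to leave between two consecutive steps of Visit 1, and a twofold titre difference that staff could not select on directly, because sera are tested later. The documents support neither input.

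**Conclusion.** The concern holds as a defect in the written allocation procedure. On the plain wording of Protocol 5.3.6, in an open-label trial with no concealed refill route described, a replacement's arm is known before enrolment. Selection of replacements could then reach the primary comparison. This conclusion rests on reading the randomization group as the arm and on the absence of any other stated mechanism.

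The size is unknown and probably small, because randomization and first vaccination occur at the same visit. The GMT factors above are illustrations under assumed rates and differences, not estimates of bias. The correction is worth making because the rule's only stated purpose, keeping 2:1:1, has almost no statistical value to set against the lost concealment.

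**What to change.** In Protocol 5.3.6, replace the same-arm rule with wording such as: *A participant who withdraws after randomization and before dosing is made up by enrolling one further participant in that site and age stratum, who receives the next unused concealed allocation. The vacated allocation is not reused.* Add a matching sentence to SAP 4.3, and report pre-dose withdrawals by arm in the SAP 8.1 flow chart. No change is needed to keep the withdrawn person in ITT, since SAP 6.1 already does so.

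This removes selection of replacements. It does not remove bias from arm-related withdrawal: those who leave are still absent from the primary analysis. If a fraction f of an arm leaves and differs from those who stay by d log2 units, the arm's GMT is displaced by the same 2^(f × d). Reporting withdrawals by arm lets readers judge that.

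The cost is one or two sentences and a final split that may differ from 2:1:1 by a few participants, with negligible loss of precision.

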5.4 Study Schedule, Procedures, & Evaluations

5.4.1 Schedule of events and data collection

Persons meeting the proposed eligibility criteria (**Section 5.3.1**) will be recruited. Written/electronic informed consent will be obtained from study participants/participant's legally authorized representative(s) (LAR) prior to conducting any study procedures.

Table 1: Schedule of Events						
Procedure	Visit 1	Follow-up Survey (Reactogenicity)	Visit 2	Follow-up Survey (Weekly ARI)	Visit 3	Visit 4
	Clinic	Phone/Email	Clinic	Phone/Email	Clinic	Clinic
Estimated Study Day (Relative to Visit 1)	0	3 and 31	28	Weekly	56	180
Time Following Visit 1 (Days) [Window]	0	3 [± 3]	28 [28-42]	Weekly		
Time Following Visit 2 (Days)		3 [± 3] (groups ii and iii only)			28 [28-92]	152 [± 30]
Informed consent & Medical Release of Information	X					
Review Eligibility Criteria	X					
Review Temporary Delay Criteria	X		X			
Demographic and Health History	X					
Influenza and COVID-19 Vaccination History	X					
Randomization	X					
Administer cclIV4 vaccine	Groups i and ii		Group iii			
Administer Moderna COVID-19 vaccine	Groups i and iii		Group ii			
Whole blood collection for sera sample	Up to 10 mL		Up to 10 mL		Up to 10 mL	Up to 10 mL
Whole blood collection for PBMC and plasma sample	Up to 24 mL [adults] or 8 mL [children]		Up to 24 mL [adults] or 8 mL [children]		Up to 24 mL [adults] or 8 mL [children]	Up to 24 mL [adults] or 8 mL [children]
Obtain solicited adverse events at 3 days following Visits 1 and 2		X				

Table 1: Schedule of Events						
Procedure	Visit 1	Follow-up Survey (Reactogenicity)	Visit 2	Follow-up Survey (Weekly ARI)	Visit 3	Visit 4
	Clinic	Phone/Email	Clinic	Phone/Email	Clinic	Clinic
Estimated Study Day (Relative to Visit 1)	0	3 and 31	28	Weekly	56	180
Time Following Visit 1 (Days) [Window]	0	3 [± 3]	28 [28-42]	Weekly		
Time Following Visit 2 (Days)		3 [± 3] (groups ii and iii only)			28 [28-92]	152 [± 30]
Obtain change in health status requiring hospitalization				X		
Obtain ARI information				X		

Visit 1; study day 0 – Screening, Enrollment, Specimen Collection and Vaccination – Clinic Visit

- Review and confirm study eligibility
- Obtain written/electronic informed consent and assent (if applicable, children age 6-11 years) and release of medical record information
- Obtain information on preferred method of contact for follow-up (text or email)
- Obtain demographic and medical history including history of influenza and COVID-19 vaccination via enrollment questionnaire
- Take temperature and review temporary delay criteria
- Collect whole blood for sera sample (**Section 5.5.4.1**) and PBMC and plasma samples (in subset of participants, target n=250; 200 adults and 50 children) (**Section 5.5.4.2**)
- Randomize study participant to intervention (2:1:1) using a permuted block method stratified by site:
 - i. concomitant administration of the mRNA COVID-19 vaccine and quadrivalent influenza vaccine
 - ii. sequential administration of the quadrivalent influenza vaccine at Visit 1 (day 0) and the mRNA COVID-19 vaccine at Visit 2 (day 28)

- iii. sequential administration of the mRNA COVID-19 at Visit 1 (day 0) followed by the quadrivalent influenza vaccine at Visit 2 (day 28).
- Administer mRNA COVID-19 vaccine and/or quadrivalent influenza vaccine (Flucelvax [ccIV4]) based on randomization scheme
- Confirm date of next appointment at Visit 2 (day 28) of study

Follow-up Survey (Reactogenicity); 3 days after vaccine administration (Visits 1 and 2) – Vaccination Reactogenicity and Safety Data – Online Questionnaire

- Automated reminders sent to all participants to complete electronic survey via participant's preferred contact method approximately 3 days after receipt of either vaccine dose administered according to study procedure (day 0 [groups i-iii] and day 28 [groups ii and iii])
- Participants/participant's LAR(s) complete brief online survey regarding vaccine reactogenicity and safety data in the three days after receipt of either vaccine dose administered according to study procedure

Follow-up Survey (ARI); weekly following Visit 1 – Weekly ARI Surveillance and Change in Health Status – Online Questionnaire

- Automated reminders sent to all participants to complete electronic survey via participant's preferred contact method once per week beginning approximately one week after Visit 1 until completion of Visit 4
- Participants/participant's LAR(s) complete brief online survey regarding new ARI episodes and change in health status requiring hospitalization throughout the entire study period
- Participants that report new ARI may provide respiratory specimens for standard point of care respiratory testing and up to 2 additional blood draws (see Table 2: Schedule of Qualifying ARI Events)

Visit 2; study day 28 (28-42) – Specimen Collection and Vaccination 2 (groups ii and iii) – Clinic Visit

Group i: Concomitant administration of mRNA COVID-19 vaccine and quadrivalent influenza vaccine

- Take temperature and review temporary delay criteria
- Collect whole blood for sera sample (**Section 5.5.4.1**) and PBMC and plasma samples (in subset of participants, target n=250; 200 adults and 50 children) (**Section 5.5.4.2**)
- Confirm date of next appointment on day 56 of study

Group ii: Sequential administration of quadrivalent influenza vaccine then mRNA COVID-19 vaccine

- Take temperature and review temporary delay criteria
- Collect whole blood for sera sample (**Section 5.5.4.1**) and PBMC and plasma samples (in subset of participants, target n=250; 200 adults and 50 children) (**Section 5.5.4.2**)
- Administer mRNA COVID-19 vaccine
- Confirm date of next appointment on day 56 of study

Group iii: Sequential administration of mRNA COVID-19 vaccine then quadrivalent influenza vaccine

- Take temperature and review temporary delay criteria
- Collect whole blood for sera sample (**Section 5.5.4.1**) and PBMC and plasma samples (in subset of participants, target n=250; 200 adults and 50 children) (**Section 5.5.4.2**)
- Administer quadrivalent influenza vaccine (Flucelvax [cclIV4])
- Confirm date of next appointment on day 56 of study

Visit 3; study day 56 (56-120) – Specimen Collection – Clinic Visit

- Collect whole blood for sera sample (**Section 5.5.4.1**) and PBMC and plasma samples (in subset of participants, target n=250; 200 adults and 50 children) (**Section 5.5.4.2**)
- Confirm date of next appointment on day 180 of study

Visit 4; study day 180 – Specimen Collection – Clinic Visit

- Collect whole blood for sera sample (**Section 5.5.4.1**) and PBMC and plasma samples (in subset of participants, target n=250; 200 adults and 50 children) (**Section 5.5.4.2**)

Table 2: Schedule of Qualifying ARI Events		
Procedure	Acute Visit	Convalescent Visit
	Clinic	Clinic
Estimated Study Day	< 10 days after symptom onset	28 days after Acute Visit
Time Following Acute Visit (Days) [Window]	0	28 [28-42]
Nasal swab collection for viral testing	X	
Whole blood collection for sera sample	X	X

Table 2: Schedule of Qualifying ARI Events		
Procedure	Acute Visit	Convalescent Visit
	Clinic	Clinic
Estimated Study Day	< 10 days after symptom onset	28 days after Acute Visit
Time Following Acute Visit (Days) [Window]	0	28 [28-42]
Whole blood collection for PBMC and plasma sample	X	X

Acute Visit; <10 Days after Symptom Onset – Specimen Collection – Clinic Visit

If a participant reports ARI symptoms at any point during the weekly electronic follow-up survey (ARI), they may be asked to complete an acute visit. These specimens may be drawn at the same time as scheduled visits 1-4.

- Obtain nasal/throat swab (**Section 5.5.4.3**)
- Obtain sera sample (**Section 5.5.4.1**), PBMC, and plasma sample (**Section 5.5.4.2**)
- Schedule convalescent visit 28 (28-42) days after acute visit for influenza or SARS-CoV-2 positive participants
- Confirm contact information and preferred method of contact for follow-up (telephone, text, or email)

Convalescent Visit, 28 (28-42) days after acute visit – Specimen Collection – Clinic Visit

If a participant tests positive for influenza and/or SARS-CoV-2 at any acute clinic visit, a convalescent visit is required 28 (28-42) days after their acute clinic visit. These specimens may be drawn at the same time as scheduled visits 1-4.

- Obtain sera sample (**Section 5.5.4.1**), PBMC, and plasma sample (**Section 5.5.4.2**)

5.4.2 Randomization

Permuted block randomization stratified by age group (children aged 6-11 years and adults aged 18-64 years) and site will be used at each site to ensure even allocation to each study arm. At each site, participants will be randomized 2:1:1 to receive: (i) concomitant administration of a mRNA COVID-19 vaccine and a quadrivalent influenza vaccine (cclIV4), (ii) sequential administration of a quadrivalent influenza vaccine (cclIV4) at Visit 1 (day 0) and a mRNA COVID-19 vaccine at Visit 2 (day 28), and (iii) sequential administration of a mRNA COVID-19 vaccine at Visit 1 (day 0) and a quadrivalent influenza vaccine (cclIV4) at Visit 2 (day 28). The project statistician will generate the randomization schemes which will be uploaded to REDCap. Participants will be randomized through REDCap with treatment allocation recorded

on the case report form. In the event that REDCap is unavailable, participants will be manually randomized through the use of sealed envelopes with randomization allocations enclosed. The project statistician will prepare envelopes that will use the same randomization strategy as the primary scheme embedded in REDCap. When an unblinded team member is informed of the age group, they will pull the next envelope in order. To capture the allocation per subject, a separate form in REDCap will be used by the unblinded study personnel to add the assignment. Sites will need to keep a log capturing these instances. The next available sequential study-number will be assigned to each enrolled participant upon study-entry.

